**C.5. Measurements.** HVP *Assessment Workers* (registered nurses who can draw blood) who enroll families into standard HVP services, have been trained to screen and recruit eligible families for the proposed project. They will administer the assessments (English or Spanish; **Table 6**) in the families’ homes or at the HVP clinic (as needed) at baseline/enrollment, and after 6mo and 12mo of services. *Home visitors* will be trained to gather interim (objective) weight measurements for the purpose of generating more frequent data points, triangulated with the assessment workers’ measurements.

**Medical and family history.** A thorough family history and physical examination will be conducted at baseline. We will collect demographic data, including socioeconomic status (education, income, eligibility for SNAP).

**Infant growth & waist trajectories.** Weight will be measured on a digital scale (Tanita) accurate to the nearest 5g. Length will be measured to the nearest 0.1 cm using an infanto-meter using the standardized WHO approach,

Table 6. Assessment time points (month of intervention) and key measures							
	Baseline	3	6	9	12	15	18
COVARIATES							
Demographics, household composition, medical history, post-partum depression, activity readiness	X						
MOTHERS							
Weight/height, waist circumference	X	X	X	X	X	X	X
Blood and vitals	X						X
24h diet & activity recall	X		X				X
Feeding and food insecurity	X		X				X
Social support and networks	X		X				X
Home environment	X		X				X
INFANTS							
Weight/length, waist circumference	X	X	X	X	X	X	X
Blood (finger prick)	X						X
24h diet & activity recall (from mother)	X		X				X

including use of staff training modules. Weight and length will be used to calculate weight-for-length and weight-for-age z-scores (WHO Standards), as recommended by the CDC for children <24 mos. Infant growth rates will be examined as the change in WLZ from baseline to follow up (12mo) Waist circumference will be measured at the umbilicus (nearest 1-mm) using a non-stretch measuring tape.

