**Aim 1 (maternal/infant outcomes).** Change in weight-related outcomes over the 2-year implementation is the primary outcome comparison. We will use multilevel regression models adjusting for clustering effect of home visitors to compare differences in the main outcomes across time by intervention arm. Regression model can be treated as a special case of path model without mediators. These regression models will include all participants, who have at least 2 measurements, regardless of when the measurements are taken, increasing the follow-up of study participants and statistical power. Specific measures relevant to Aim 1 are maternal and children weight-related measures. These models will allow the evaluation of intervention effects on, for example, child growth trajectory and activity, and mother BMI, metabolic, and behavior outcomes. Investigation of the main effects of COPE on outcomes will be conducted at each follow-up. Baseline outcome measures will be treated as covariates to control for potential

baseline differences. Effects of COPE will be evaluated first at each follow-up assessment point. Longitudinal analyses with all follow-up points (6 and 12 months) will then be conducted to examine profiles across time to investigate the effects of program conditions on trends of outcome measures.

**Aim 2 (maternal transmission).** To estimate the mediational effects of maternal transmission, multilevel path models will be developed and evaluated per our hypotheses. The model specification will be guided by our conceptual model treating Intervention program as the distal variables along with demographic variables to affect mother's weight, diet and behavior as mediators, which in turn may influence infants' outcome. While the intervention program will be at the Level-2 unit, all other variables included in the multilevel path models will be Level-1 variables obtained from mothers and children. Using breastfeeding and maternal diet on infants' weight trajectories as an example, the mediation mechanism of maternal transmission can be expressed by the process: COPE → breastfeeding \* maternal diet → weight. The path model will allow the test of both the direct effect of COPE on infant weight trajectory and its indirect effect on through breastfeeding and maternal diet.

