**Power Analysis Aims 1-3 (Figure 7).** A total of 30 home visitors will be recruited and randomized to HVP or HVP+COPE. With an average of 13 families served by each visitor, a total of 300 families will be invited to participate in the proposed study over 12 months. Based on our pilot work and existing HVP data, we expect a retention rate of 75% of families, which will result in a final sample of 200 mothers/infants. We have calculated power using G\*Power based on an effective sample of N=200 for the main weight related outcomes with the design of repeated measurement. All tests use a two-sided alpha level of .05. Our pilot study showed a small to medium effect size of .4 (Cohen's *d*) on our main outcome of children's weight velocity and smaller effect on energy intake at 6 months post-test. No previous study has investigated the long-term (12 months) delivery of in-home obesity prevention on 0-2yo children's growth trajectory, diet and activity. However, an in-home intervention compared to outpatient pediatric counseling resulted in a large effect size of 1.64 (Cohen's *d*) for changes in zBMI at 12 months, among obese 2-5yo children. To account for potential large clustering effect at the home visitor level, we assume the intraclass correlation (ICC) of .05 to .1 with inflation factors  $(1+(n-1)*ICC)$  of 1.4 to 1.8, respectively. After taking inflation factor into account, our proposed sample size of 200 will have enough power to detect medium effect sizes based on Cohen's *f* between .17 and .20. More comprehensive path model will be specified in each aim for model evaluation and hypothesis testing. We are aware of the sample size limitation and will be cautious in the number of variables and the size of the model involved. We used the hypothesis-testing framework of RMSEA to estimate power of model fitting in our study. With  $\alpha = .05$ , a null hypothesis RMSEA of .00 (almost exact fit for path model), an alternative hypothesis RMSEA of .08 (criterion of not acceptable models) and degrees of freedom (size of the model) ranging from 10 to 15, the range of statistical power for a sample size of 300 is between .83 and .93. We will have sufficient power to detect small to medium effect of a set of pre-selected parameters associated with mediators and outcomes with sample size of 200.

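### The Aim 1 primary comparison spreads over at least six unadjusted tests at two-sided .05 if one infant and one maternal measure both count, with no order and no rule for what counts as success

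*Combined protocol and SAP*

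**What the plan says.** All references are to the combined protocol and SAP.

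- **Error rate.** C.6, Power Analysis: "All tests use a two-sided alpha level of .05". No later sentence qualifies this.
- **Primary comparison.** C.6, Aim 1: "Change in weight-related outcomes over the 2-year implementation is the primary outcome comparison". The outcomes are plural and belong to two persons: "Specific measures relevant to Aim 1 are maternal and children weight-related measures".
- **Repeated testing.** C.6, Aim 1: "Investigation of the main effects of COPE on outcomes will be conducted at each follow-up". The order of work is "Effects of COPE will be evaluated first at each follow-up assessment point", after which "Longitudinal analyses with all follow-up points (6 and 12 months) will then be conducted".
- **Candidate measures.** C.5, for infants: "Weight and length will be used to calculate weight-for-length and weight-for-age z-scores (WHO Standards"), plus waist circumference. Table 6, for mothers: "Weight/height, waist circumference".
- **Competing labels.** The power paragraph calls children's weight velocity the main outcome. C.5 describes infant growth as change in weight-for-length z-score (WLZ) to 12 months. Aim 1 mentions maternal BMI as an example.
- **Horizon.** The general strategy in C.6 has waves at baseline, 6 and 12 months. Table 6 runs to 18 months, Table 7 schedules an 18-month assessment, and Aim 1 speaks of two years.

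The document contains no multiplicity adjustment, test hierarchy, gatekeeping step or definition of a successful primary result.

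**The concern.** Specific Aim 1 says its results will show whether home visiting works as a vehicle for preventing obesity in infants and in mothers, and section B.1 expects them to inform public policy. A conclusion of that weight needs a stated rule linking test results to the claim. As written, each outcome is tested at two follow-ups and again longitudinally, each time at the full .05, for two persons and an unstated number of measures. The overall chance of a spurious positive is therefore above .05 and is not controlled. A reader of the final report could not tell whether, say, one nominally significant 6-month maternal result was meant to count. Naming the infant measure more precisely would not settle this, because the maternal outcomes and the repeated tests would remain.

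**Working it through.** **Stated figures.** The .05 is an input, and the plan gives no family-wise rate to reproduce. The nearest figure is the detectable Cohen's f of .17 to .20 at N = 200, after inflation by 1.4 to 1.8. For a two-group repeated-measures test I used λ = f²·N·m / (1 + (m − 1)ρ), with m waves and correlation ρ between waves.

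- f = .17, N = 200/1.4 = 142.9, m = 3, ρ = .3: λ = 4.13 × 1.875 = 7.74, power 78.9%.
- f = .20, N = 200/1.8 = 111.1, m = 3, ρ = .3: λ = 4.44 × 1.875 = 8.33, power 81.6%.

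The figures are thus consistent with a repeated-measures test at about 80% power, but m, ρ and the 80% target are my assumptions. With ρ = .5 the powers are 69.6% and 72.5%. With one time point and no baseline adjustment (λ = 4.13 and 4.44) they are about 52% and 55%.

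**Counting tests.** Each outcome is tested at 6 months, at 12 months and at least once longitudinally, which makes three tests. One infant and one maternal measure give 2 × 3 = 6. Two measures per person give 4 × 3 = 12.

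**If the tests were independent.** P(at least one false positive) = 1 − .95^k.

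- k = 3: 14.3%
- k = 6: 26.5%
- k = 12: 46.0%

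For jointly normal two-sided tests these values are upper limits.

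**If the tests are correlated.** The tests share families and time points, so they are correlated. I simulated multivariate normal z-statistics under no effect (1,000,000 draws per setting) and counted any |z| > 1.96. The assumed correlations are .5 to .8 between 6 and 12 months, .1 to .3 between mother and infant, and .5 to .9 between two measures on one person; time and outcome correlations are multiplied. The longitudinal test is either the average of the two time points or their difference (trend), because Aim 1 does not fix the contrast.

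| Primary measures | 6 and 12 months plus average | 6 and 12 months plus trend |
|---|---|---|
| One infant | 7.9% to 9.7% | 11.8% to 12.3% |
| One infant, one maternal | 14.9% to 18.4% | 21.7% to 22.9% |
| Two infant, two maternal | 20.2% to 31.2% | 28.9% to 37.9% |

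For one infant and one maternal measure, the two time points alone give 14.7% to 17.3%. An average adds at most about one point; a trend adds about 5.5 to 7 points.

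**After the fix.** Take a fixed order of infant test, then maternal test, each at .05. If the infant null is true, any false positive requires rejecting it, which has probability .05. If it is false, only the maternal test can err, again with probability at most .05. The family-wise rate is therefore at most 5%.

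**The case against.** Four points can be made for the plan.

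**The size is not a document figure.** This stands. The plan states neither the number of primary variables nor any correlation. A reader might merge the two-measure and four-measure cases and quote one false-positive rate for the trial. The documents do not support that: they do not say which family applies. Six tests, for instance, cannot exceed 26.5%.

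**There is no rule that any single significant test wins.** This also stands. A reader might infer such a rule from the uniform .05, but the power section only sets alpha, and Specific Aim 1 refers to the results collectively. If infant and maternal success were both required, the error would not inflate in this way across the two persons. The defect is that no decision rule is given, so neither reading can be excluded.

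**Infants and mothers are separate questions.** The plan distinguishes primary prevention (infants) from secondary prevention (mothers), and the power paragraph names only a child measure as main. Giving each person a separate .05 is defensible. The rate for one measure is then about 8% to 12%, well below the pooled figures but still above 5% because of the repeated tests.

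**The longitudinal analysis adds little.** This is true if it estimates an average effect and not if it tests a trend. Aim 1 speaks of trends.

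**Conclusion.** The concern holds. C.6 applies two-sided .05 to every test, while its primary comparison covers infant and maternal weight-related outcomes at two follow-ups and again longitudinally, without order, adjustment or success rule. On each reading examined the chance of a false positive exceeds 5%:

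- about 8% to 12% with one infant measure only;
- about 15% to 23% with one infant and one maternal measure (26.5% if the six tests were independent);
- about 20% to 38% with four measures.

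The direction follows from the text. The sizes depend on the assumed correlations and on whether the longitudinal test is an average or a trend, and should be quoted as illustrations. This is more than missing detail, because carrying out the plan as written leaves the error rate uncontrolled. It should be settled before any outcome comparison by arm, since an order chosen afterwards protects nothing.

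**What to change.** Amend the Aim 1 and power paragraphs of C.6.

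1. First reconcile the assessment horizon (12 months, 18 months or two years) across C.6, Table 6 and Table 7, so that the final assessment is a single defined time.
2. Name one primary test at two-sided .05: the COPE effect on infant WLZ change from baseline to that assessment, estimated from the baseline-adjusted multilevel repeated-measures model. This keeps the longitudinal model that the power paragraph relies on and removes the competing weight-velocity label.
3. Test maternal BMI at the same assessment, at two-sided .05, only if the infant test is significant.
4. Report the 6-month contrasts, separate trend tests and all other Aim 1 outcomes as secondary, with confidence intervals and no success claim.

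The change needs no extra families and no split of alpha. Its main cost is that maternal and 6-month results cannot support a confirmatory claim if the infant test fails. The detectable effect should also be restated for the named contrast, because an f of .17 to .20 reads as a repeated-measures figure; an unadjusted test at one time point would have only about 52% to 55% power at those values, which baseline adjustment would raise.

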*The proposed study builds upon the momentum, resources, and research infrastructure of our pilot work to test the larger-scale and sustained impact of COPE on infant's and mothers' obesity outcomes, and to study key mechanisms of maternal and social transmission on infants' obesity risk.* Specifically, 300 low-income mothers/infants enrolled in Healthy Families America HVP will be recruited and enrolled in the study, for an effective final sample of 200 mothers/infants. Based on standard HVP procedures, mothers/infants will be matched to highly trained home visitors (nurses) based on their ethnicity/race and language preferences. Home visitors, in turn, will be randomly assigned to deliver the standard HVP curriculum only or the standard HVP curriculum + COPE as part of their weekly home visits for two years of HVP services. Comprehensive assessments of mothers/infants will be conducted at enrollment and after 6 and 12 months of intervention.

**Specific Aim 1 (maternal and infant outcomes).** Test the direct effects of COPE on infants and mothers' weight, metabolic risks, diet/energy intake, and physical activity. This will be accomplished by comparing changes in body weight, metabolic markers, and eating and activity-related behaviors between infants/mothers across study arms (HVP only vs. HVP+COPE). These results will indicate whether HVP is an effective infrastructure for primary and secondary obesity prevention.

**Specific Aim 2 (maternal transmission).** Test whether breastfeeding and maternal diet and activity, feeding practices, and food insecurity mediate the effect of COPE on infants' outcomes. This aim will test mechanisms of maternal transmission on infants' obesity risks.

**Specific Aim 3 (social transmission).** **Aim 3** is two-pronged. **Aim 3a** tests the direct effect of HVP+COPE (vs. HVP only) on the characteristics of the social and community networks that surround mothers and infants (i.e., the density, composition, and quality of "health support networks"). **Aim 3b** tests whether the characteristics of social networks mediate the effects of COPE on maternal and infant outcomes. These findings will indicate if HVP obesity prevention efforts can alter and/or activate social network mechanisms.

**Secondary Aim.** Conduct a real-life economic analysis (costs, cost-savings, and non-monetary benefits) of integrating COPE into existing HVPs.

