## PROTECTION OF HUMAN SUBJECTS

### A. Participants

This comparative effectiveness research involves the enrollment of 300 mothers/infants for a final effective sample of 200 mothers and their infants (age 6mo at enrollment).

**Inclusion of women.** Women are represented by mothers and female infants, which will be about half of the infant sample. Based on our projected effective sample of 200 mothers and their 200 infants (N=400), we anticipate that 75% of our sample will be women (100 children + 200 mothers = 300).

**Inclusion of racially and ethnically diverse families.** The families enrolled in the Home Visiting Program (HVP) from which the sample is drawn is culturally, racially and ethnically diverse, reflecting the population of low-income families enrolled in home visiting services in the Antelope Valley, CA area. Based on our HVP partner (Healthy Families America site in Southern California: Antelope Valley Partners for Health and Children's Bureau) clients' demographics and on our pilot work, we anticipate the following ethnic and racial distribution: 70% Hispanic/ Latino, 13% African American, 8% White, 5% American Indian/Alaskan, and 4% mixed/other race.

It is important to note that Health Families America (HFA) home visitors are matched to families based on language and cultural background. Home visitors are rigorously trained to understand, acknowledge, and respect families' cultural differences. Home visitors are selected because of their personal characteristics (i.e. non-judgmental, compassionate, ability to establish a trusting relationship, etc.), their experience working with culturally diverse communities, and their skills to do the job.

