### C. Recruitment and Retention

**Participant recruitment.** Low-income mothers and their infants (N=300, for a final effective sample of 200) will be participants in the study. Active participants will be low-income mothers and their infants (6mo-old at enrollment) drawn from mothers who are enrolled in HVP services at the Healthy Families America site/chapter in Antelope Valley, CA. Home visitors providing the HVP services will introduce the study to mothers, and study Assessment Workers will obtain written consent. Home visitors will clarify with mothers that their refusal to participate in the study is not affecting the services they provide. In our experience from our pilot research, families feel comfortable to refuse if they do not wish to participate. Of note, 90% of families receiving *Healthy Families America* HVP services choose to enroll in enhancement studies when offered (i.e., when a module is added to the core curriculum and evaluated). These rates are consistent with our pilot work.

**Inclusion/exclusion criteria.** Participants will be ineligible if either parent and/or child have a Dx of eating disorders (e.g., Anorexia Nervosa), Schizophrenia or Obesity-related syndrome (e.g., Prader Willi). Participants enrolled in a weight-loss program will be ineligible.

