**Retention.** Using conservative estimates, we anticipate that 25% of mothers enrolled will drop out of home visiting services over the 12-month study. Consequently, we will oversample at enrollment (N=300) to ensure an effective sample of 200 mothers and infants. We have learned a great deal about retaining mothers through our prior pilot studies. We attribute retention in part to our persistent efforts and abilities of the HVP home visitors, but also believe that there are unique features of home visited mothers that facilitate retention in a research study. For example, many of these mothers are socially isolated, and opportunities to exchange with their home visitor can be highly rewarding for mothers. We will use multiple strategies to retain the sample over the 12months of the implementation and assessments. We will rely on approaches widely used in studies of high-risk populations: (1) a gift card in the amount of \$25 at each data collection, with all incentives paid after each assessment/data collection *regardless of whether they complete the study*; (2) frequent contact with participants to maintain engagement because we believe that open communication between the team and participants is critical; (3) quarterly newsletters to update participants about study activities; (4) acknowledging birthdays; (5) participants are given a reminder phone call the day before the weekly visits and assessment sessions (or on Fridays for Monday assessment sessions).

**Informed consent procedure.** Informed consent, approved by the appropriate IRB, will be obtained by Antelope Valley Partners for Health assessment workers who are trained by our research team. All mothers that are enrolled in HFA's HVP services by Antelope Valley Partners for Health and Children's Bureau will receive a detailed explanation of the protocol, including any potential benefits and risks (in English or Spanish). Mothers will be required to sign the consent form (in Spanish or English) and provide consent for their infants. Only participants from whom consent is obtained will be involved in the study. Signed consents will be kept in the participants' files in locked filing cabinets. Each participant will receive a copy.

**Waiver.** No waiver or modification of consent is being requested from the IRB.

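### The model-fit power of .83 to .93 does not follow from its stated N of 300 (the inputs give .87 to .96), and no figure is given for the final sample of 200, where it is .67 to .81

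*Combined protocol and SAP*

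**What the plan says.** Section C.6 (Power Analysis Aims 1-3) uses the RMSEA hypothesis-testing framework to give power for model fit. The inputs are alpha .05, null RMSEA .00, alternative RMSEA .08 and model degrees of freedom from 10 to 15. The result is that "the range of statistical power for a sample size of 300 is between .83 and .93".

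The same section says that "a total of 300 families will be invited to participate in the proposed study" and that "we expect a retention rate of 75% of families, which will result in a final sample of 200 mothers/infants". Its G*Power calculation for the weight outcomes uses 200. For the path models at 200 it says only that power is sufficient for a set of pre-selected parameters; no number is given. It also acknowledges a sample size limitation, without quantifying it.

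Other sections treat 300 as the number enrolled:

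- Specific Aims: "300 low-income mothers/infants enrolled in Healthy Families America HVP will be recruited and enrolled in the study".
- Protection of Human Subjects, A. Participants: the study "involves the enrollment of 300 mothers/infants for a final effective sample of 200 mothers and their infants".
- C. Recruitment and Retention: "we will oversample at enrollment (N=300) to ensure an effective sample of 200 mothers and infants".

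**The concern.** Every input the RMSEA power formula needs is given, so the stated range should be reproducible. If it is not, then the N or some other input is misreported.

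The choice of N is a separate matter. The plan calls 200 its effective sample in several places and uses it for Aim 1, but gives fit power only at 300. This is the only numerical power figure specific to the path models that carry Aims 2 and 3. Low fit power means that a badly fitting mediation model is more likely to pass unnoticed. The plan says it will restrict model size because of the sample. If that lowers the degrees of freedom, this power falls further, so the figure at 200 bears on how large the models should be.

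**Working it through.** **Inputs** (all from C.6, Power Analysis): alpha .05; null RMSEA 0; alternative RMSEA .08; df 10 to 15; N=300 as stated; final sample 200.

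**Formula.** Under the null the fit statistic is central chi-square, so the critical value is its .95 quantile: 18.307 for df 10 and 24.996 for df 15. Under the alternative it is noncentral chi-square with λ = (N − 1) × df × .08². Power is the probability that this variable exceeds the critical value.

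**The plan's own figure, N=300.**

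- df 10: λ = 299 × 10 × .0064 = 19.136; power .873, against .83 stated.
- df 15: λ = 299 × 15 × .0064 = 28.704; power .957, against .93 stated.

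The stated range is not reproduced.

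**Other readings at N=300 (df 10 / df 15).**

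- N in place of N − 1: .875 / .958
- alpha .025: .807 / .925
- alpha .10: .928 / .979
- reversed test (null .08, alternative .00): .857 / .958
- null RMSEA .01: .858 / .949
- null RMSEA .02: .808 / .919
- two-group form: .518 / .650
- N divided by 1.4: .710 / .841
- N divided by 1.8: .573 / .710

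None comes within 2 points at both ends. An alternative RMSEA of about .076 would (.829 / .931), but the plan gives .08. At N=300 no whole number of degrees of freedom gives .83 (df 8 gives .809, df 9 gives .844).

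**Which N fits.** Scanning N from 190 to 329, power rounds to .83 at df 10 and .93 at df 15 only for N = 269 to 274.

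**Power by N, before clustering.**

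| N | df 10 | df 11 | df 12 | df 13 | df 14 | df 15 |
|---|---|---|---|---|---|---|
| 300 | .873 | .897 | .917 | .933 | .946 | .957 |
| 270 | .828 | .856 | .879 | .899 | .916 | .930 |
| 225 | .736 | .768 | .796 | .821 | .844 | .863 |
| 200 | .672 | .705 | .734 | .761 | .786 | .808 |

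The row for 225 is 75% of 300. For .80 power, 255 families are needed at df 10, 206 at df 14 and 197 at df 15.

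**A possible source of the stated pair (inference only).** C. Recruitment and Retention says that 90% of families receiving "HVP services choose to enroll in enhancement studies when offered".

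- 300 × .90 = 270.
- 270 / 30 visitors = 9 families each, so the inflation factors are 1 + 8 × .05 = 1.4 and 1 + 8 × .10 = 1.8. These match the stated factors "of 1.4 to 1.8, respectively".
- 270 × .75 = 202.5, close to 200, whereas 300 × .75 = 225.

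An N of 270 would therefore explain the power range, the inflation factors and the final sample together. But the plan never states 270, gives an average of 13 families per visitor, and elsewhere calls 300 the enrolled number.

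**The case against.** The strongest reply is that little depends on the figure. At 300 the plan understates its power, no sample size is derived from it, and the Aim 1 calculation is separate and already uses 200. That is correct, and it limits the weight of the point.

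A second reply is that 200 may not be the analysed N. The plan specifies intention-to-treat with multiple imputation and/or full information maximum likelihood, so dropouts could contribute to the path models; and 75% of 300 is 225, not 200. This stands in part. At 225 the range is .74 to .86, still below what is stated. But incomplete cases do not carry full information, the plan does not offer this as its reason for using 300, and it names 200 as its effective sample.

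Third, the visible text sets no .80 target, and fit power is not what Aims 2 and 3b chiefly need, which is power for mediation. Both are fair: .80 is used here only as a conventional yardstick. Neither removes the mismatch between the stated power and its inputs, or the absence of a figure at 200.

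Finally, a single-level formula is only indicative for a multilevel path model. That is so, and it applies equally to the plan's own number.

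**Conclusion.** The concern holds. As written, the power of .83 to .93 is wrong for N=300: the inputs give .87 to .96, and the stated pair belongs to an N of 269 to 274. At the plan's final sample of 200 the fit power is .67 to .81, below .80 for df 10 to 14, and the plan does not report it.

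These values rest on the standard noncentral chi-square formula, the plan's own RMSEA values and degrees of freedom, complete data on N families, and no clustering. Clustering by visitor may lower the power; the plan does not give enough to say by how much. The arithmetic is certain. The explanation through N=270 is conjecture, and the conclusion does not depend on it. The consequence is confined to the stated power of the path models for Aims 2 and 3.

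**What to change.** 1. Make the N and the power agree: either .87 to .96 for a sample of 300, or .83 to .93 for a sample of about 270 if that was the N used.
2. Add a sentence such as: At the expected final sample of 200, power to reject a model misfitting at RMSEA .08 is .67 (df 10) to .81 (df 15), before any allowance for clustering by visitor, which may lower it; this is not power for the indirect effects in Aims 2 and 3b.
3. If imputation or full information likelihood is the reason for using a larger N, say so. If 225 is the number expected to be retained, give .74 to .86 for it.
4. Reconcile the counts (300 invited or enrolled, 90% uptake, 75% retention, 200 final) across the Specific Aims, C.6, and the Participants and Recruitment and Retention sections.

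The cost is one formula re-run and one or two sentences, plus the alignment of the counts. The stated power at the final sample becomes less favourable. Enrolment and the Aim 1 analysis do not change.
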